9.3 Definitions

9.3.1 Adverse Event

An adverse event (AE) can be any unfavorable and unintended sign (including an abnormal laboratory finding, for example), symptom, or disease temporally associated with the use of medicinal (investigational) product, whether or not the AE is considered related to the medicinal (investigational) product.

An adverse event can therefore be any of the following:

- Any unfavorable and unintended sign (including an abnormal laboratory finding), symptom, or disease temporally associated with the use of a medicinal product, whether or not considered related to the medicinal product
- Any new disease or exacerbation of an existing disease (a worsening in the character, frequency, or severity of a known condition)
- Recurrence of an intermittent medical condition (e.g., headache) not present at baseline
- Any deterioration in a laboratory value or other clinical test (e.g., ECG, X-ray) that is associated with symptoms or leads to a change in study treatment or concomitant treatment or discontinuation from Study Drug
- Adverse events that are related to a protocol-mandated intervention, including those that occur prior to assignment of study treatment (e.g., screening invasive procedures such as biopsies)

9.3.2 Adverse Drug Reaction and Unexpected Suspected Adverse Drug Reaction

Adverse Drug Reaction (ADR)

In the *pre-approval* clinical experience with a new medicinal product or its new usages, particularly as the therapeutic dose(s) may not have been established, ADR is defined as follows:

All noxious and unintended responses to a medicinal product related to any dose should be considered adverse drug reactions.

The phrase "responses to a medicinal product" means that a causal relationship between the medicinal product and the adverse event has been determined as at least a reasonable possibility, i.e., the relationship cannot be ruled out.

Suspected Unexpected Adverse Drug Reaction

A suspected unexpected ADR is any ADR, the nature or severity of which is not consistent with the Reference Safety Information in the applicable Investigator's Brochure.

A suspected adverse reaction implies a lesser degree of certainty about causality than an adverse reaction.

9.3.3 Serious Adverse Event (SAE)

A serious adverse event is any adverse event that in the view of either the Investigator or Sponsor, meets any of the following criteria:

- Results in death
- Is life threatening: that is, poses an immediate risk of death at the time of the event

An AE or suspected adverse reaction is considered "life-threatening" if, in the view of either the Investigator or Sponsor, its occurrence places the subject at immediate risk of death. It does not include an AE or suspected adverse reaction that, had it occurred in a more severe form, might have caused death

- Requires inpatient hospitalization or prolongation of existing hospitalization
Hospitalization is defined as an admission of greater than 24 hours to a medical facility and does not always qualify as an AE
- Results in a persistent or significant incapacity or substantial disruption of the ability to conduct normal life functions
- Results in a congenital anomaly or birth defect in the offspring of the subject (whether the subject is male or female)
- Important medical events that may not result in death, are not life-threatening, or do not require hospitalization may also be considered serious when, based upon appropriate medical judgment, they may jeopardize the subject and may require medical or surgical intervention to prevent one of the outcomes listed in this definition. Examples of such medical events include allergic bronchospasm requiring intensive treatment in an emergency room or at home, blood dyscrasias or convulsions that do not result in inpatient hospitalization, or the development of drug dependency or drug abuse.

The terms "severe" and "serious" are not synonymous. Severity refers to the intensity of an adverse event (e.g., rated as mild, moderate, or severe or according to the criteria in Section 9.4.4.2); the event itself may be of relatively minor medical significance (such as severe headache without any further findings).

Severity and seriousness need to be independently assessed for each adverse event recorded on the eCRF.

9.3.4 Medically Attended Adverse Event (MAAE) and New Onset of Chronic Disease (NOCD)

An MAE is an AE that leads to an unscheduled visit (including a telemedicine visit) to a healthcare practitioner (HCP). This would include visits to a study site for unscheduled assessments (e.g., rash assessment, abnormal laboratory follow-up) and visits to or from HCPs external to the study site (e.g., urgent care, primary care physician).

MAAE are adverse events with medically attended visits, such as visits for hospitalization, an emergency room or doctor's clinic visit, or an otherwise unscheduled visit to or from medical personnel for any reason. They do not include routine study visits.

Should an MAAE lead to the new diagnosis of a chronic medical condition that was not present or suspected prior to enrollment, this will be categorized as a new onset of chronic disease (NOCD).

9.3.5 Adverse Event of Special Interest

An adverse event of special interest (AESI), including both serious or non-serious events, is one of scientific and medical concern specific to the Sponsor's product or program, for which ongoing monitoring and rapid communication by the Investigator to the Sponsor could be appropriate.

Adverse events of special interest, if defined in the study protocol or associated documents, are required to be reported by the Investigator to the Sponsor immediately, no more than 24 hours after the Investigator's first knowledge of the event.

No AESIs are specified for this study.

9.3.6 Targeted Medical Event

Other targeted medical events (TMEs), or other adverse event of interest (OAEI), are AEs, including both serious or non-serious events, that may be defined in the study protocol or associated documents for further characterisation or evaluation of product specific adverse events.

No TMEs are specified for this study.

9.3.7 Clinical Events of Special Interest

Clinical Events of Special Interest (CESI) are events relating to the detection of disease (SARS-CoV-2) activity relevant to the study vaccine. These events are analyzed separately from safety data; however, if the CESI demonstrates untoward signs or symptoms, this event will also be reported as an AE.

To be considered as a CESI of COVID-19 the following case definition must be met:

- The subject must have experienced at least TWO of the following systemic symptoms: Fever ($\geq 38^{\circ}\text{C}$), chills, myalgia, headache, sore throat, congestion or runny nose, nausea, diarrhoea, new olfactory and taste disorder(s), OR
- The subject must have experienced at least ONE of the following respiratory signs/symptoms: cough, shortness of breath or difficulty breathing, OR
- Clinical or radiographical evidence of pneumonia; AND
- The subject must have at least one test positive for SARS-CoV-2 by PCR.

To be considered as a CESI of asymptomatic SARS-CoV-2 infection, a subject who demonstrates none of the COVID-19 symptoms described above but who tests positive for SARS-CoV-2 on PCR test or anti-nucleocapsid antibody test (if nucleocapsid antibody negative prior to entry into the study) will be counted.

Reporting requirements for confirmed COVID-19 cases are described in Section [9.5.5](#).

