	
• Mild: The event is easily tolerated by the subject and does not affect the subject's usual daily activities• Moderate: The event causes the subject more discomfort and interrupts the subject's usual daily activities• Severe: The event is incapacitating and causes considerable interference with the subject's usual daily activities 
Cases of PCR confirmed COVID-19 and PCR-confirmed or serologically confirmed asymptomatic SARS-CoV-2 infection will be recorded as Clinical Events of Special Interest (CESI). These events will not be regarded as adverse events and will be analyzed separately from safety data (Sections 9.3.7 and 9.5.5). PCR confirmed COVID-19 disease will be graded as follows:
 
• Mild: No requirement for supplemental oxygen to maintain oxygen saturation $\geq 93\%$• Moderate: Oxygen supplementation at a concentration of $< 50\%$ required to maintain oxygen saturation $\geq 93\%$• Severe: Oxygen supplementation at a concentration of $> 50\%$ or any form of mechanical ventilatory support required 
Immunogenicity
 
Immunogenicity measures include mean titer, GMT and GMFR in neutralising antibody titer to SARS CoV-2 spike protein and anti-spike protein IgG titer and the proportion of subjects seroconverting. Descriptive statistics, by assessment time point, will be used to describe these results. Statistical testing, if performed, will be prespecified in the final statistical analysis plan and will be exploratory in nature.
 
SARS-CoV-2 neutralising antibody titer will be tested using a clinical isolate of SARS CoV-2 (hCoV-19/Singapore/2/2020) in BSL-3 settings on an in vitro plaque reduction neutralisation test (PRNT) and/or pseudovirus neutralization test and/or surrogate virus neutralization test (sVNT) and/or microneutralization test. Testing using other SARS-CoV-2 isolates may also be performed.
 
Total IgG against the full-length SARS-CoV-2 recombinant spike protein and/or spike protein subunits will be assessed using an immune-Luminex and/or ELISA assay.

--	---

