Male subjects: In the event that the female partner of a male subject that has received ARCT-021 becomes pregnant, the progress of the pregnancy of the male subject's partner should be followed until the outcome of the pregnancy is known (i.e., delivery, elective termination, or spontaneous abortion). If the pregnancy results in the birth of a child, the Study Center and Sponsor may follow-up with the mother and may request access to the mother and infant's medical records to obtain additional information relevant to the pregnancy progress and outcome. A longer follow-up may be required if a newborn child experiences a medical condition. Follow-up will be performed to the extent permitted by the applicable regulations and privacy considerations; e.g., partner informed consent form may be required.

9.5.5 Cases of PCR-confirmed COVID-19 or PCR/Serologically Confirmed SARS-CoV-2 Infection Without COVID-19

Any case of PCR-confirmed COVID-19 will be regarded as a Clinical Event of Special Interest (Section 9.3.7) and must be reported to the Sponsor or designee within 24 hours of the site learning of this event.

In addition, CESIs must be reported for all cases detected for up to one year after receipt of vaccination with ARCT-021, including events reported by participants who have early

terminated study ARCT-021-01 or study ARCT-021-02 and participants who did not roll over to the ARCT-021-02 study if these events fall within the 1 year timeframe.

Whilst the subject is enrolled in the study reporting will be performed by completion of a ‘COVID-19 and SARS-CoV-2 Infection Report Form’ in the EDC (Section 9.4.1). For subjects that have terminated early from the study but not withdrawn consent, cases of PCR-confirmed COVID-19 and PCR/serologically confirmed SARS-CoV-2 infection without COVID-19 will be reported via a paper COVID-19 and SARS-CoV-2 Infection Report Form, which should be faxed or emailed to the Sponsor or designee. The reporting instructions, including the fax number and email address for submitting paper forms can be found in the Investigator site file for the study.

The EDC and paper reporting forms will collect the following parameters:

- Whether PCR test and/or anti-nucleocapsid antibody test are positive
- COVID-19 symptoms
- Oxygen saturation on air
- Percent supplemental oxygen required (if any)
- Type of assisted ventilation required (if any)
 - CPAP
 - External Ventilation
 - Invasive Ventilation
 - Other (specify)

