10.5.5 Clinical Events of Special Interest Analyses

Statistical analyses of CESIs will be descriptive over timepoint in the safety and longitudinal safety populations. These endpoints include confirmed COVID-19 (including severe cases) and asymptomatic SARS-CoV-2 infection over timepoint and also analyzed as pooled and separately for the younger and older adult groups.

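### The two CESI classes in Protocol 9.3.7 are not exhaustive, so the COVID-19 and asymptomatic counts need not add up to the confirmed infections

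*Protocol*

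**What the plan says.** Protocol 9.3.7 gives a case definition for each class.

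- **COVID-19.** The clinical part has three alternatives. The first is "The subject must have experienced at least TWO of the following systemic symptoms", followed by a list that includes fever, headache and sore throat. The second is "The subject must have experienced at least ONE of the following respiratory signs/symptoms: cough, shortness of breath or difficulty breathing". The third is clinical or radiographic pneumonia. The laboratory part is "The subject must have at least one test positive for SARS-CoV-2 by PCR".
- **Asymptomatic infection.** This covers "a subject who demonstrates none of the COVID-19 symptoms described above" and whose PCR or anti-N test is positive, the antibody route being open only to subjects who were anti-N negative before entry.

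The synopsis (Statistical Considerations) names the same two classes. Protocol 10.5.5 says of the CESI analysis: "These endpoints include confirmed COVID-19 (including severe cases) and asymptomatic SARS-CoV-2 infection over timepoint".

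Other sections draw the line elsewhere. Protocol 9.5.5 covers infection without COVID-19, which is wider than asymptomatic infection. For subjects who left the study early, for example, "cases of PCR-confirmed COVID-19 and PCR/serologically confirmed SARS-CoV-2 infection without COVID-19 will be reported via a paper" form. SAP 8.1.8 describes CESIs only in general terms, with listings and narratives and no case definition. SAP 7.3 censors immunogenicity data on any positive PCR, or on anti-N at or above 5,000 AU/ml, whatever the symptoms.

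**The concern.** Two classes that look like symptomatic and asymptomatic infection should between them cover every confirmed infection. These do not, because the lower bound of one is not the complement of the other. COVID-19 starts at two systemic symptoms while asymptomatic infection stops at zero. COVID-19 accepts PCR only, while asymptomatic infection also accepts serology.

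The uncovered cases can arise under the protocol's own procedures. Under 6.2.4, exposure to a confirmed case is enough to call for a PCR, so a subject with a single symptom can be tested and found positive. Appendix 2 allows anti-N testing on retained serum, and SAP 7.2 includes the N-antigen in the multiplex assay, so serology can reveal an infection in someone who had symptoms but no PCR at the time.

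At stake is whether the reported infection counts reconcile with each other, with the report forms, and with the subjects censored for infection. Protocol Table 2 names enhanced respiratory disease after infection as a risk to be followed, so a complete count of infections has some safety interest.

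**Working it through.** The plan states no figure to reproduce. The check is whether the two definitions cover every laboratory-positive profile.

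**Inputs (Protocol 9.3.7)**

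- Systemic symptoms: 0, 1, or 2 and more (3 levels)
- Respiratory sign: no or yes (2 levels)
- Pneumonia: no or yes (2 levels)
- Laboratory result: PCR positive with anti-N negative, PCR positive with anti-N positive, or anti-N positive only (3 states)

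All subjects are taken as anti-N negative before entry. Number of profiles: 3 × 2 × 2 × 3 = 36, of which 24 are PCR positive and 12 are positive by anti-N only.

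**Rules, read literally**

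- COVID-19 = (at least 2 systemic, or a respiratory sign, or pneumonia) and PCR positive
- Asymptomatic = no listed item at all, and (PCR positive or anti-N positive)

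**Two cases worked through**

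1. Headache only, PCR positive. Systemic count 1 is below 2, with no respiratory sign and no pneumonia, so this is not COVID-19. Headache is on the list, so it is not asymptomatic either.
2. Cough and fever, new anti-N positivity, no positive PCR. The clinical part of COVID-19 is met but the PCR part is not. Symptoms are present, so it is not asymptomatic.

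**All profiles, under three readings**

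| Reading | Unclassified, PCR positive (of 24) | Unclassified, anti-N only (of 12) | Total (of 36) |
|---|---|---|---|
| Literal | 2 | 11 | 13 |
| None read as not meeting the symptom criteria | 0 | 10 | 10 |
| PCR requirement attached to pneumonia only | 2 | 3 | 5 |

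On the literal reading, the 2 are the one-symptom profile with anti-N negative or positive. The 11 are the 12 anti-N-only profiles less the one with no listed item. This treats pneumonia as a listed item; if it is not a symptom, the profile with pneumonia alone and anti-N only becomes asymptomatic and 13 becomes 13 − 1 = 12. The lenient reading closes the one-symptom hole but not the serology hole. The third reading would let symptoms alone qualify as COVID-19, and it still leaves a gap.

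**The same subject across sections**

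| Place | Positive PCR, one systemic symptom | New anti-N, symptoms, no positive PCR |
|---|---|---|
| Protocol 9.3.7, synopsis, 10.5.5 | Neither named class (literal reading) | Neither named class |
| Protocol 9.5.5 form | Can be captured | Can be captured |
| SAP 7.3 censoring | Infected | Infected, if at least 5,000 AU/ml |

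**The case against.** The case on the other side is substantial.

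- **A reader might infer that 10.5.5 analyses only two classes.** It does not say so. Its wording is inclusive, and a further category is not ruled out. But none is prespecified, and 9.3.7 does not make these events CESIs.
- **A reader might infer that these infections vanish from the record or from the tables.** The documents do not support that. The 9.5.5 form collects PCR, anti-N and symptoms, so a total can be derived. SAP 8.1.8 lists and narrates every CESI under a broad description that could take these cases in. The SAP's adverse event summaries contain no CESI count table, and this SAP covers an interim analysis only, so the layout of the final tables cannot be seen.
- **A reader might infer that vaccine-related infection incidence is understated.** Infection incidence is not among the primary, secondary or exploratory endpoints in 1.2, there is no comparator group and no hypothesis is tested. No efficacy estimate is at risk.
- **Requiring PCR for COVID-19 is a legitimate choice.** Symptoms that meet the threshold in 6.2.4 should trigger a PCR, which limits serology-only symptomatic cases. This stands, but the choice calls for somewhere else to put such cases.
- **Adverse event reporting is a backstop.** Only in part. Appendix 1 restricts recording after Day 29 to SAE, CESI, NOCD and MAAE, and to those categories throughout for subjects not vaccinated in this study. The rule in 9.3.7 that symptomatic events are also adverse events presupposes that the event is a CESI.

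These arguments limit the consequence. They do not close the definitional gap.

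**Conclusion.** The concern holds as a definitional defect. The one-symptom hole depends on taking none literally. The serology hole follows from the definition as written and remains, in whole or in part, under each reading tested. As a result, the COVID-19 and asymptomatic counts need not sum to the confirmed infections, and a subject can be infected for SAP 7.3 while belonging to neither named CESI class.

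The size in subjects cannot be derived. The documents give neither an expected number of infections nor a distribution of symptoms, and 13 of 36 must not be read as a proportion of cases. With about 99 and at most 166 subjects planned (Protocol 3.6), one or two unplaced cases would be visible in a descriptive table if infections are few; that is an assumption. The effect is confined to descriptive CESI summaries and does not reach the primary or secondary endpoints. The correction is worth making because it is cheap and because assigning such cases after seeing them, in an open-label study, is best avoided.

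**What to change.** Reconcile Protocol 9.3.7, 9.5.5, 10.5.5 and SAP 8.1.8 around one exhaustive scheme:

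- (a) COVID-19, as now defined;
- (b) laboratory-confirmed SARS-CoV-2 infection (PCR or new anti-N) not meeting (a), split into no listed symptoms and any listed symptoms;
- (c) total infections = a + b.

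State the anti-N positivity rule once. SAP 7.3 uses 5,000 AU/ml without requiring a negative result before entry, whereas 9.3.7 requires the negative result and gives no threshold. Unless these are aligned, total (c) will not match the censored subjects. Align the synopsis with the same classes.

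SAP 5.1 rules out changes to the interim SAP once data are pulled, so the scheme belongs in the SAP for the final analysis, before final database lock.

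The cost is wording and one or two table rows; the 9.5.5 form already collects the data. One caveat should be printed with the table: serology on stored samples does not date the infection, so the symptom split for serology-only cases is approximate.

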9.4 Monitoring and Recording Adverse Events

Any pre-existing conditions or signs and/or symptoms present in a subject prior to the first injection of ARCT-021 should be recorded as Medical History and not recorded as AEs unless the pre-existing condition worsened. The Investigator should always group signs and symptoms into a single term that constitutes a **single unifying diagnosis** if possible. Before a diagnosis is confirmed, all symptoms should be reported as separate AEs.

Any AE that includes a new diagnosis of a chronic medical condition that was not present or suspected prior to enrollment, will be categorized as a new onset of chronic disease (NOCD).

9.4.1 Serious Adverse Events

In the interest of subject safety, and in order to fulfill regulatory requirements, all SAEs (regardless of their relationship to Study Drug) should be reported to the Sponsor or designee within 24 hours of the Study Center's first knowledge of the event.

For subjects that received ARCT-021 in the parent study, the collection of SAE will begin at the Screening visit, when SAE (and MAAE) occurring since completion of the Parent Study will be solicited to ensure continuity of safety follow-up from the Parent Study to this study, and stop at the end of the subject's follow-up period which is defined as the subject's last protocol-specified study visit.

For subjects who receive ARCT-021 in this study and who did not receive ARCT-021 in the Parent Study, the collection of SAEs will begin after the subject has received ARCT-021 and stop at the end of the subject's follow-up period. SAEs that occur prior to administration of ARCT-021, including those that occurred between leaving the Parent Study and dosing in this Study, will be recorded as medical history.

SAEs considered to be related or possibly related to Study Drug and any deaths will continue to be reported for 30 days after the subjects last study visit. SAEs will be reported within the electronic data capture system (EDC) whenever possible. If the EDC is not available, the SAE can be initially reported using a paper Initial Serious Adverse Event Form, which should be faxed or emailed to the Sponsor or designee. The SAE reporting instructions, including the fax number and email address for submitting paper forms can be found in the Investigator site file for the study. If the Investigator is reporting by telephone, it is important to speak to someone in person versus leaving a message.

Detailed information should be actively sought and included on Follow-Up Serious Adverse Event Forms as soon as additional information becomes available. All SAEs will be followed until resolution. SAEs that remain ongoing past the subject's last protocol-specified follow-up visit will be evaluated by the Investigator and Sponsor. If the Investigator and Sponsor agree the subject's condition is unlikely to resolve, the Investigator and Sponsor will determine the follow-up requirement.

